4.5 Management of Toxicities and Dosage Modifications

Table 3 provides the recommended dose modifications for toxicities (graded using NCI CTCAE version 5.0) in AML.

Table 3: Recommended Dose Modifications

Event	Occurrence	Action
Hematologic Toxicities		
Grade 4 neutropenia with or without fever or infection; or Grade 4 thrombocytopenia	Occurrence prior to achieving remission	Transfuse blood products, administer prophylactic and treatment anti-infectives as clinically indicated. In most instances, study treatment should not be interrupted due to cytopenias prior to achieving remission.
	Occurrence after achieving remission and lasting at least 7 days	Delay subsequent study treatment cycle and monitor blood counts. Administer granulocyte colony-stimulating factor (G-CSF) if clinically indicated for neutropenia following consultation with the Medical Monitor. Once the toxicity has resolved to a clinically acceptable situation, resume study treatment at the same dose and schedule (no dose reductions permitted after completion of lead-in cohort.)

Suggested doses of supportive care therapies are provided; however, adjustment of the dosages based on the patient's clinical condition or each institution's standard of care is permitted.

Patients will be provided with a diary to track diarrheal episodes and doses of required concomitant medications (ie, antibiotics, antivirals, antifungals, allopurinol, phosphate binders, etc). The diary should be brought to every clinic visit so study staff can monitor compliance.

4.5.1 Management of Nonhematologic Toxicities

Adverse events may be treated with concomitant medications, as deemed clinically indicated by the Principal Investigator. All concomitant medications must be recorded in the source and on the appropriate CRF.

Adverse events that are moderate to severe in intensity (see [Appendix C](#) for toxicity grading) and considered possibly or probably related to study drug treatments may result in the delay or termination of study treatment in affected patients.

4.5.1.1 Hyperkalemia and Tumor Lysis Syndrome

Tumor lysis may occur as part of initial cytoreductive therapy. The most extreme form, known as Tumor Lysis Syndrome (TLS), is characterized by hyperkalemia, hyperuricemia, hyperphosphatemia, increased lactate dehydrogenase (LDH), coagulopathy, and a potential cytokine release

syndrome. ***Due to an increased likelihood of TLS, hospitalization of patients with monocytic differentiation and/or a peripheral blast count of >10,000/mm³ is strongly recommended for the first dose of alvocidib (ie, Cycle 1 / Day 1).***

- Mandatory IV hydration with 0.45% NaCl (or similar hydration fluid per institutional standard) sterile solution at **250-500 cc** for 1-2 hours prior to alvocidib, then an additional **250-500 cc** for 1-2 hours after alvocidib during Cycle 1 (optional for subsequent cycles for patients who have achieved a CR).
- Replacement of excessive fluid losses, including from diarrhea, should be done unless otherwise clinically indicated.
 - Alvocidib is known to induce mild diarrhea during treatment days. Over-the-counter measures are typically effective in this setting if initiated early. Persistent diarrhea despite optimal outpatient management would trigger medical consultation. Early consideration should be given for possible *Clostridioides difficile* (*C. difficile*) infection in this patient population and identifying/treating as expeditiously as possible should be top of mind (see [Section 4.5.1.2](#)).
- Mandatory oral allopurinol to be started at least 72 hours prior to Day 1 of Cycle 1 and continued until completion of the first cycle (ie, 28 days). This may be discontinued for subsequent treatment cycles if uric acid levels are within normal limits and there is no evidence of TLS.
- Mandatory oral phosphate binder to be started at the same time as initiation of IV hydration on Day 1 of Cycle 1 and continued for the first week (ie, 7 days).
 - If serum phosphorus levels are <3 after the first treatment with alvocidib and there is no evidence of TLS, phosphate binders may be discontinued. Patients should continue to be monitored for TLS as outlined for subsequent treatment cycles. Caution is warranted for patients who still have a high blast count as they remain at risk for TLS with subsequent treatments.
- Evaluation of laboratory indicators of TLS during initial therapy (may be adjusted for subsequent cycles based on extent of tumor burden):
 - Tumor lysis laboratory evaluations ('tumor lysis labs') include electrolytes (sodium, potassium, chloride, and carbon dioxide) as well as creatinine, calcium, lactate dehydrogenase (LDH), uric acid, and phosphorus levels.
 - During Cycle 1, monitor tumor lysis labs prior to alvocidib infusion and 2 hours (\pm 30 minutes) after completion of IV hydration post alvocidib. Labs will also be drawn daily for the first three days

following the first alvocidib dose (ie, Days 2-4) and at least weekly for the remainder of Cycle 1.

- During Cycles 2+, tumor lysis labs will be assessed prior to each dose of alvocidib

Risk of TLS and Guidelines for Management

TLS management during treatment with alvocidib was implemented in previous studies, which included medical prophylaxis for hyperuricemia, as well as aggressive monitoring and management of hyperkalemia and other biochemical laboratory abnormalities. Rapid development of hyperkalemia has been of particular concern in earlier studies with the hybrid dosing regimen of alvocidib. While these guidelines are not necessarily consistent with specific standard recommendations for the treatment of TLS, they are recommended based on previous experience with the treatment of patients with the hybrid dosing regimen of alvocidib. These measures resulted in a lower incidence of TLS without adverse outcomes.

For this reason, Investigators are encouraged to follow the recommended guidelines below but may follow your own institution's protocols in determining the best treatment for your patients.

- If potassium levels are increasing to >4.0 mEq/L, patients should receive a 30 gm dose of sodium polystyrene sulfonate, unless there are other likely causes of hyperkalemia other than TLS or contraindication to its use.
- If potassium levels rise to >5.0 mEq/L, in addition to the 30-gm dose of sodium polystyrene sulfonate, patients should also receive 10 units of IV rapid-acting insulin and 25 gm (1 ampule) of IV dextrose 50%, unless there are other likely causes of hyperkalemia other than TLS or contraindication to its use. Investigators are strongly encouraged to consider patient hospitalization for inpatient monitoring and follow up.
- If potassium levels rise to >5.5 mEq/L, patients should be considered for emergent intermittent or continuous dialysis.
- Calcium supplementation should only be given for symptomatic hypocalcemia in this setting to avoid renal precipitation of calcium phosphate crystals.
- Patients who develop clinical evidence of cytokine release syndrome or who have hyperkalemia requiring dialysis will receive immediate steroid therapy with an equivalent of at least 20 mg of IV dexamethasone.

4.5.1.2 Diarrhea

Alvocidib is known to induce mild diarrhea during the days of treatment. Over-the-counter measures are typically effective in this setting if initiated early. At the first signs of diarrhea, patients should initiate loperamide (or equivalent) 2 mg by mouth every 2 hours during the waking hours (not to exceed 16 mg/day). Once the diarrhea is controlled, the time interval of loperamide may be titrated to a frequency that adequately controls the diarrhea. The diarrhea observed with alvocidib almost always resolves following completion of therapy, so treatment with loperamide following completion of therapy will not be required in most patients. If loperamide (or equivalent) does not control diarrhea, cholestyramine (or equivalent) 5 gm orally for 4 times daily may be added. If diarrhea is not controlled with the above prophylactic regimen and is Grade 2 or greater, patients should contact the clinic and study drug treatment should be held until diarrhea has resolved. Should diarrhea persist beyond Cycle 1, patients should undergo testing for *C. difficile*. Should testing indicate the presence of *C. difficile*, appropriate antibiotics targeting this infection should be initiated. Should testing exclude the presence of *C. difficile*, diarrhea prophylaxis similar to Cycle 1 should be continued in subsequent cycles. Replacement of excessive fluid losses should be done unless otherwise clinically indicated.

4.5.1.3 Nausea/Vomiting

Antiemetics (ie, 5-hydroxytryptamine [5-HT3] receptor inhibitor or other antiemetic medications) are permitted according to standard practices at each investigational site.

4.5.1.4 Infection Prevention

Prophylactic antibiotics including levofloxacin (or equivalent) 500 mg orally once daily and azole antifungals (ie, fluconazole, posaconazole, voriconazole, isavuconazole) should be administered to patients in all treatment arms if ANC <500/ μ L. These can be discontinued when the ANC \geq 500/ μ L per institutional standards and physician discretion. Valacyclovir (or equivalent) to be administered **once daily (QD) or twice daily (BID)** to all patients throughout the study based on institutional standard unless there are contraindications. **Other similar antiviral agents may be administered per institutional standards with dosing according to each medication's full prescribing information.**

Donor lymphocyte infusions are not allowed at any time during the study.

4.5.2 Management of Hematologic Toxicities

Adverse events that are moderate to severe in intensity (see [Appendix C](#) for toxicity grading) and considered possibly or probably related to study drug treatments may result in the termination of study treatment in the affected study patient. Such termination should be reviewed with the Sponsor's Medical Monitor at the earliest possible time (see [Section 8.5](#)). Following review with the Sponsor's Medical Monitor, the study patient may be permanently withdrawn from the study depending upon the nature and severity of the event.

Adverse events may be treated with concomitant medications, as deemed clinically indicated by the Principal Investigator. All concomitant medications must be recorded on the appropriate CRF.

4.6 Concomitant Medications and Therapies

4.6.1 Previous Therapies

During Screening, patients will be asked about all medications used during the previous 30 days from anticipated first dose. This information will be recorded in the source documentation and appropriate CRF along with the diagnosis or reason for use. If a branded product is being taken, the generic name should be reported, if known.

Patients will not be enrolled into the study if they received any previous treatment with alvocidib or any other CDK inhibitor or receive other antileukemic therapy within the past **2 weeks or 3-5 half lives of the prior therapy, whichever is less.**

4.6.2 Concomitant Therapies

Concomitant therapies are any new or existing medications or therapy taken by the patient including:

- Drugs, including but not limited to, prescription, over-the-counter, birth control pills/patches/hormonal devices, and homeopathic preparations
- Nondrug therapies, including but not limited to, thermal/laser/radiation procedures, vitamins, herbal medicines/supplements.

During the Screening process (up to 2 weeks prior to anticipated first dose of study drug), information on all concomitant therapies, medications, and procedures will be recorded in the source documents and appropriate CRF along with the diagnosis or reason for use.

Once the patient receives the first dose of study drug, recording of concomitant therapies will be limited to any new medication or modification of an existing medication taken for treatment of an adverse event (AE). These therapies will be recorded in the source documents and appropriate CRF along with the diagnosis or reason for use. Those therapies used for the treatment of an adverse event are to be linked to an AE and documentation of the AE must also be completed (refer to [Section 8](#)).

If a branded product is being taken, the generic name should be reported, if known.

4.6.2.1 Mandated / Permitted Therapies

Concomitant medications necessary for the health and well-being of the patient and that do not interfere with study assessments are permitted during the study at the Investigator's discretion. This includes the use of appropriate medications for the treatment of AEs and/or concurrent illnesses under the direction of the Principal Investigator. All such therapies must be recorded in the source and on the appropriate CRF.

In patients with rapidly proliferating disease, hydroxyurea may be administered up to the evening before starting treatment in either Stage, but not within 12 hours prior to dosing. ***After the first dose, hydroxyurea may continue to be used per investigator discretion.***

Patients may be allowed on study if they have undergone a diagnostic lumbar puncture (LP) for suspected CNS leukemic involvement. If, at the time of the LP, they received a single dose of intrathecal (IT) chemotherapy, that patient would still be considered eligible for this study so long as the LP was negative for CNS disease. Should the LP indicate positive cytology necessitating continued IT therapy, the patient would be ineligible for study inclusion.

Investigators are permitted to administer IT chemotherapy per institutional protocols. The administration of prophylactic dose of IT chemotherapy during a diagnostic LP is permitted once only.

Routine growth factor support is not allowed. Granulocyte colony-stimulating factor (G-CSF) may be administered for Grade 4 neutropenia (with or without fever or infection) if the event occurs after the patient has achieved remission of at least 7 days' duration (Table 3) and following consultation with the Medical Monitor. Once the toxicity has resolved to a clinically acceptable situation, study treatment should resume at the same dose and schedule. No dose reductions are permitted after completion of the lead-in safety cohort.

Medications and procedures that are mandatory or permitted during the study are listed in [Section 4.6](#).

4.6.2.2 Prohibited Therapies

The following medications are excluded from concomitant use:

- Antileukemic therapy (chemotherapy, radiation therapy, immunotherapy) within the last **2 weeks or 3-5 half lives of the prior therapy, whichever is less**, prior to the first study drug administration and during the cycle of study treatment.

4.6.3 Birth Control Requirements for Fertile Patients

Sexually active patients and their partners must use an effective method of contraception associated with a low failure rate prior to study entry, for the duration of study participation, and for at least 3 months (males) and 6 months (females) after the last dose of study drug. The following are considered effective contraceptives: (1) oral contraceptive pill; (2) condom plus spermicide; (3) diaphragm plus spermicide; (4) abstinence; (5) patient or partner surgically sterile; (6) patient or partner more than 2 years post-menopausal; or (7) injectable or implantable agent/device.

4.7 Protocol Deviations

It is expected that this study will be conducted as described in this protocol, except for an emergency situation in which the protection, safety, and well-being of the patient requires immediate intervention, based on the judgment of the Principal Investigator (or a responsible, appropriately trained and credentialed professional[s] designated by the Principal Investigator). In the event of a significant deviation from the protocol due to an emergency, accident or error, the Principal Investigator or Designee must contact the Sponsor at the earliest possible time by telephone. This will allow an early joint decision to be made as to whether or not the patient should continue in the study. This decision will be documented in writing by both the Principal Investigator and the Sponsor.

4.8 Other Precautions

Based on observed nonhematologic and hematologic toxicities and laboratory abnormalities, dose adjustments for patients **enrolled only in the lead-in cohort** will be made according to the dose de-escalation plan outlined in [Appendix F](#).

5. ON-STUDY CLINICAL AND LABORATORY EVALUATIONS

See [Appendix A](#) - Schedule of Activities.

5.1 Screening

5.1.1 Within 2 Weeks Prior to First Dose of Alvocidib

- Obtain written informed consent
- Collect and document a complete medical history including pathological confirmed diagnosis of AML by WHO criteria, and all other measures of disease and disease symptoms (eg, extramedullary disease)
- Collect information about any transfusions that have occurred within 56 days prior to Cycle 1 Day 1
- Perform a complete physical examination including height (cm) and weight (kg)
- Assess ECOG PS ([Appendix B](#))
- Record vital signs (temperature, heart rate, systolic and diastolic blood pressures, and respiratory rate)
- Collect bone marrow and peripheral blood
 - Collect bone marrow and peripheral blood samples for confirmation of diagnosis, cytogenetic profiling, and PD tests ([Section 7.3](#)).
 - Collect bone marrow sample to be sent to a central laboratory for MRD assessment using standardized techniques (ie, MPFC and molecular testing including NGS) ([Appendix D](#))
 - If patient is enrolled, 6 to 8 bone marrow slides will be prepared and sent to the Sponsor. Details regarding the collection and shipping of these slides is provided in the Laboratory Manual.
- Perform 12-lead electrocardiogram (ECG)
- Record all concomitant medications including all prescription drugs, nonprescription drugs, and nutritional supplements taken within the past 2 weeks
- Collect urine or serum sample for beta-human chorionic gonadotropin (β-hCG) pregnancy test for females of childbearing potential

- Collect blood for evaluation of laboratory parameters ([Appendix D](#)):
 - Hematology: complete blood count (CBC) with differential and platelet count
 - Full serum chemistry panel.
- Perform lumber puncture (LP) in patients with suspected CNS involvement

5.1.2 Within 72 Hours Prior to First Dose of Alvocidib

Perform the following activities and evaluations within 72 hours prior to administration of the first dose of alvocidib:

- Record all concomitant medications including all prescription drugs, nonprescription drugs, and nutritional supplements
- Collect urine or serum sample for β-hCG pregnancy test for females of childbearing potential
- Collect blood for evaluation of laboratory parameters ([Appendix D](#)):
 - Hematology
 - Full serum chemistry panel
- Collect urine sample for full urinalysis
- Review all Inclusion/Exclusion criteria and determine if patient has met all eligibility criteria for inclusion into the study
- Start administration of allopurinol orally daily at least 72 hours prior to study treatment.
- Provide patient with study diary and instruct them on daily completion. Remind patient to bring diary back at every clinic visit.

5.2 Cycle 1

5.2.1 Cycle 1: At Least 2 Hours Prior to First Dose

Perform the following procedures at least 2 hours prior to starting therapy on Day 1 (unless otherwise stated):

- Abbreviated physical examination including weight (kg) for calculation of body surface area (BSA)
- Assess ECOG PS ([Appendix B](#))
- Record all concomitant medications including all prescription drugs, nonprescription drugs, and nutritional supplements taken since screening

- Initiate supportive care measures prior to first dose in all patients to minimize the likelihood of tumor lysis syndrome:
 - Administer pretreatment IV hydration, oral allopurinol, and oral phosphate binder (see [Section 4.5.1.1](#))
 - Replacement of excessive fluid losses, including from diarrhea, should be done unless otherwise clinically indicated ([Section 4.5.1.2](#) and [Section 4.5.1.3](#))

5.2.2 Cycle 1: Day 1 Just Prior to First Dose

Perform the following procedures just prior to dosing on Day 1:

- Record vital signs measured 15-30 minutes prior to the initiation of infusion following a 5-minute rest
- Collect blood for baseline laboratory parameters ([Appendix D](#)): Results are not required to be reviewed prior to treatment.
 - Tumor lysis labs: sodium, potassium, chloride, carbon dioxide, creatinine, calcium, lactate dehydrogenase (LDH), uric acid, and phosphorus
 - Coagulation labs: fibrinogen level.
- Collect urine or serum sample for β -hCG pregnancy test for females of child-bearing potential if screening pregnancy test is greater than 72 hours prior to first dose. Results must be reviewed prior to treatment.

5.2.3 Cycle 1: Dosing Days: Arm 1: Days 1, 3-12, 15; Arm 2: Days 1, 8, 15

A ± 2 -day window will be allowed for Day 15 of both treatment arms. A ± 1 -day window will be allowed for Day 8 (Arm 2 only).

- Abbreviated physical examination (Arm 1: Days 8 and 15; Arm 2: Days 8 and 15)
- Assess ECOG PS (Arm 1: Days 8 and 15; Arm 2: Days 8 and 15) ([Appendix B](#))
- Record vital signs on Days 1, 8, and 15 of both arms
- Record only those medications (prescription, nonprescription, nutritional supplements) administered in conjunction with an AE
- Assess patient for adequate hydration at all study visits and replace excessive fluid losses, including from diarrhea, unless otherwise clinically indicated ([Section 4.5.1.2](#) and [Section 4.5.1.3](#))
- Collect blood for evaluation of laboratory parameters ([Appendix D](#)): hematology and full serum chemistry panel on each day of alvocidib administration and twice weekly (minimum of 72 hours between collections) during LDAC treatment (ie, Days 3-12 of Arm 1)
- Monitor tumor lysis labs according to [Section 4.5.1.1](#)

- Monitor fibrinogen levels as clinically indicated
- Administer prophylactic antibiotics, antivirals, and antifungals according to [Section 4.5.1.4](#)
- Assess for AEs
- Administer alvocidib and/or cytarabine according to [Section 4.4.2](#)
- Review study diary and remind patient to bring diary back at next clinic visit

Stage 2 dosing regimen will be selected based on results from Stage 1 arms in terms of response rates, relative safety, and risk-benefit ratio.

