	
Supportive Care (Stage 1 and Stage 2)
 
Supportive care will be provided including:
 
• Tumor Lysis Prevention and Treatment
○ Due to an increased likelihood of TLS, hospitalization of patients with monocytic differentiation and/or a peripheral blast count of >10,000/mm³ is strongly recommended for the first dose of alvocidib (ie, Cycle 1 / Day 1).○ Mandatory IV hydration with 0.45% NaCl (or similar hydration fluid per institutional standard) sterile solution at 250-500 cc for 1-2 hours prior to alvocidib, then an additional 250-500 cc for 1-2 hours after alvocidib during Cycle 1 (optional for subsequent cycles for patients who have achieved a CR).• Replacement of excessive fluid losses, including from diarrhea, should be done unless otherwise clinically indicated.
○ Alvocidib is known to induce mild diarrhea during treatment days. Over-the-counter measures are typically effective in this setting if initiated early. Persistent diarrhea despite optimal outpatient management would trigger medical consultation. Early consideration should be given for possible Clostridioides difficile infection in this patient population and identifying/treating as expeditiously as possible should be top of mind.• Mandatory oral allopurinol to be started at least 72 hours prior to Day 1 of Cycle 1 and continued until completion of the first cycle (ie, 28 days). This may be discontinued for subsequent treatment cycles if uric acid levels are within normal limits and there is no evidence of tumor lysis syndrome.• Mandatory oral phosphate binder to be started at the same time as initiation of IV hydration on Day 1 of Cycle 1 and continued for the first week (ie, 7 days).
○ If serum phosphorus levels are <3 after the first treatment with alvocidib and there is no evidence of TLS, phosphate binders may be discontinued. Patients should continue to

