2.8 Summary of Risk and Benefits

There have been no clinical studies conducted using alvocidib post-venetoclax induction failure; however, the safety profile for alvocidib has been well-described in several clinical studies in patients with AML and appears to be acceptable in patients with nonfavorable disease characteristics. The early observation of tumor lysis and the potential for renal failure has resulted in an aggressive prophylaxis approach to manage the possible dramatic lysis of leukemic blasts caused by alvocidib. This approach in the most recent studies in patients with AML has resulted in an overall incidence of any grade TLS <30% and of any grade TLS as a serious adverse event <5% with no deaths due to TLS on study or within 30 days of the last dose of study drug. Treatment-related mortality for patients treated with alvocidib/FLAM is approximately 8-10%, with a range up to 28% in Study 6 in relapsed/refractory AML patients. Overall, TRM of alvocidib/FLAM appears to be comparable to other therapeutic options including 7+3 and intermediate- and high-dose cytarabine.

Alvocidib monotherapy (Study 3) showed acceptable safety in the relapsed/refractory AML setting with diarrhea being the dose-limiting toxicity. A single patient experienced hyperacute TLS requiring dialysis following alvocidib administration on Day 1, and subsequently died of fungal sepsis. Prophylaxis for TLS was not mandated in this study. Following this instance of hyperacute TLS, the protocol was amended to allow treatment with hydroxyurea up until the evening before alvocidib was administered (but not within 8 hours) for patients with highly proliferative disease.

The study drugs are being administered in an outpatient setting with mandatory prophylaxis with IV fluids before and after alvocidib doses along with oral allopurinol and oral phosphate binders to mitigate the risk of TLS. In addition, patients will return to the clinic daily for the first three days (72 hours) to receive each dose of alvocidib, be monitored for hydration status and clinical symptoms, and have TLS labs drawn. The starting alvocidib dose in this study is approximately one quarter of the typical starting dose used in previous clinical studies with alvocidib and patients with high circulating peripheral blast counts (ie, >30,000) are excluded from participation in hopes of mitigating the

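### The Cycle 1 Day 1 tumor-lysis results need not be read before the first alvocidib dose; reading them first would be a low-cost improvement

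*Protocol*

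**What the plan says.** Protocol 5.2.2 asks for tumor-lysis labs and fibrinogen immediately before the first infusion, with the note "Results are not required to be reviewed prior to treatment". The synopsis carries the same note. The next item in 5.2.2, a pregnancy test repeated when the screening test is too old, is handled the opposite way: its result has to be seen before dosing.

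Other parts of the protocol bear on this:

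- Section 4.5.1.1 states "During Cycle 1, monitor tumor lysis labs prior to alvocidib infusion and 2 hours" after the post-dose hydration, and further draws follow on Days 2 to 4. It then recommends graded potassium actions, from "If potassium levels are increasing to >4.0 mEq/L, patients should receive a 30 gm dose of sodium polystyrene sulfonate" up to "If potassium levels rise to >5.5 mEq/L, patients should be considered for emergent intermittent or continuous dialysis".
- Section 5.1.2 says "Perform the following activities and evaluations within 72 hours prior to administration of the first dose of alvocidib". Its list includes a full chemistry panel and the eligibility review. Appendix D shows that this panel covers every tumor-lysis analyte.
- Section 5.2.1 places the Day 1 examination and the start of supportive care at least 2 hours before dosing. Hydration is mandatory in Cycle 1; the synopsis specifies "sterile solution at 250-500 cc for 1-2 hours prior to alvocidib".
- Section 2.8 includes pre-infusion tumor-lysis labs among the measures that are meant to balance the safety risk.
- In the dose-limiting toxicity (DLT) list, the TLS item of Appendix F names *hypophosphatemia*. Section 4.5.1.1 describes TLS by *hyperphosphatemia* and mandates a phosphate binder.

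**The concern.** A sample taken as a safety measure before an exposure cannot influence that exposure if nobody has to look at it first. Chemistry can move within three days. The protocol expects some patients with rapidly proliferating disease, because section 4.6.2.1 lets them take hydroxyurea until 12 hours before dosing. No criterion in 4.3.2 or 4.3.3 limits potassium, phosphorus or uric acid, and a GFR as low as 30 mL/min is eligible.

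A patient whose potassium, creatinine, uric acid or phosphorus has worsened since the screening panel could therefore receive the first dose, as an outpatient, before the change is noticed. The hazard can appear on the first day. On the earlier monotherapy study, section 2.8 reports: "A single patient experienced hyperacute TLS requiring dialysis following alvocidib administration on Day 1".

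**Working it through.** The plan gives no figure for this point, so the check is mainly a comparison of passages, with some simple arithmetic.

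1. **Is there a contradiction?** Section 4.5.1.1 requires a pre-infusion draw in Cycle 1 but does not make its result a condition of dosing. Section 5.2.2 requires the same draw and waives prior review. The two are compatible. The pregnancy-test item shows that the authors said so explicitly when they wanted a result read first.

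2. **How old can the last seen chemistry be?** The 5.1.2 panel may be drawn up to 72 h before dosing. I assume that it is read, because the eligibility review sits in the same window; the protocol does not say so in terms. If the Day 1 sample were drawn at the 5.2.1 visit and read, its age at dosing would be about 2 h. The difference is 72 − 2 = up to 70 h. This compares a worst case with an assumed case. It measures how fresh the information is and does not measure risk.

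3. **How often does it arise?** It arises once per patient. Planned first infusions are 6 (lead-in) + 52 (Stage 1) + 76 (Stage 2) = 134. Enrolled at closure (SAP section 2) are 7 + 4 = 11, and 11/134 = 8.2%.

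4. **What does the earlier case show?** Section 2.6.2.3 gives 1 of 19 AML patients with clinical TLS. This is 5.3%, which agrees with the stated 5%; the exact 95% interval is 0.1% to 26.0%. The lowest dose level in that study was 20 + 30 = 50 mg/m² per day, against 25 mg/m² on Day 1 here, and TLS prophylaxis was not mandated. The case is context and does not estimate a rate for this trial.

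5. **Would reading the result delay the dose?** Laboratory turnaround T is not in the documents. With the draw moved to a visit about 2 h before dosing, the delay is max(0, T − 2) h: none for an assumed T of 1 or 2 h, and the excess over 2 h beyond that. With the draw left where it is, the infusion would wait the full T.

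6. **Does the phosphate word matter?** In Appendix F any one listed event is a DLT. The TLS item allows 14 days for resolution. A separate item already counts Grade 3 or 4 electrolyte imbalance that lasts more than 48 hours despite optimal management. Persistent severe hyperphosphatemia is caught by the 48-hour item first, so correcting the word reclassifies essentially no patient.

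**The case against.** The strongest case against is that this is one layer among many, set on purpose. Blast counts above 30,000/mm³ are excluded, and hospitalization is strongly recommended for higher-risk patients. Allopurinol, hydration and a phosphate binder are mandatory, and the first dose is low. Labs are repeated 2 hours after the post-dose hydration and on Days 2 to 4. The waiver is only a minimum, so an investigator may read the result first. All of this stands, and it keeps the point small.

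A reader might also infer more than the documents support:

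- *That the potassium steps of 4.5.1.1 are bypassed or made unusable before the first dose.* They need not be applied to the Day 1 value, but nothing prevents it. They are recommendations for TLS management during treatment, defer to institutional protocols, and at the two lower levels exempt hyperkalemia with another likely cause. They were not written as pre-dose gates.
- *That reading the labs would have prevented the reported hyperacute case.* Neither 2.6.2.3 nor 2.8 says that this patient's pre-dose chemistry was abnormal or unread. The amendment described afterwards concerned hydroxyurea.
- *That the phosphate word distorted DLT decisions.* The 48-hour item rules that out for practical purposes.

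**Conclusion.** The point holds as a suggestion for improvement and should not be read as a protocol error. Sections 5.2.2 and 2.8 sit awkwardly together: pre-infusion monitoring is presented as a risk measure, yet its result may go unseen until after the first dose. The gap is one unread same-day value per patient, backed by a panel that may be up to 72 hours old. It rests on the assumption that the 72-hour panel itself is read. The documents give no figure for TLS avoided, and I infer none.

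No endpoint, analysis population or statistical test is affected. The sponsor closed the study on November 17, 2020 after a portfolio review, with 11 patients enrolled, so the practical value lies in any later protocol that reuses this text. The Appendix F word is an editorial slip. It concerns the lead-in cohort, whose 7 patients the DSMB has already reviewed (SAP 7.1).

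**What to change.** Draw the Day 1 tumor-lysis labs at the start of the 5.2.1 visit, and replace the waiver in 5.2.2 and the synopsis with:

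> *Potassium, creatinine, uric acid and phosphorus must be reviewed by the investigator before the infusion starts; hold the first dose until any clinically significant abnormality or worsening since the 72-hour panel has been managed per institutional practice.*

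The hold matters because review without an action rule would achieve little. Do not import the potassium steps of 4.5.1.1 as pre-dose gates: that would mean giving sodium polystyrene sulfonate for a potassium just above 4.0 mEq/L to a patient who has not yet had alvocidib. Fibrinogen may keep the waiver.

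The change is to wording and timing, with no added sample or visit. It has two costs. The first dose may be delayed where laboratory turnaround exceeds the time already spent on site. The baseline also becomes a pre-hydration sample and is no longer the immediate pre-dose partner of the 2-hour post-hydration draw; keeping that partner would take a second sample.

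As a separate editorial correction, change *hypophosphatemia* to *hyperphosphatemia* in the TLS item of Appendix F, and leave the 48-hour electrolyte item as it is.
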